For frontal approach neurosurgical and neurointerventional procedures, the usual placement of the SedLine® sensor is challenging.

Numerous studies have already analyzed the accuracy of the change of position and the application of alternative positions for other devices used for depth of anesthesia monitoring (2,3,4,5). Albeit this, yet to date, there is no study that analyzed the application of alternative positions for the SedLine® sensors.

Research Questions and Hypotheses

The purpose of our study is to compare the standard Masimo SedLine EEG sensor frontal placement versus an experimental nasal placement of the SedLine® sensors for neuromonitoring. To determine whether this position generates similar data and validate this new alternate position.

We hypothesized that placing the central sensors in the montage approximately 2 cm below the standard recommended placement, across the nasal bridge and then running under the eyes to the normal temporal leads placement would put the entire montage out of the operative field and would still have corresponding values.

Study Design

Prospective cohort study.

Population

It is expected to recruit 40 patients undergoing general anesthesia. Considering a drop-out of 20%, we'll recruit 50 patients.

Duration of evaluation

Study participants will be evaluated only during surgery.

The study will be performed in an operation room during surgery, from the moment of induction to anesthesia up to a few minutes after the extubation. Setting up the sensor, time alignment in both Masimo Roots, as well as collecting and processing data from both sensors will be the standard approach for all 40 patients.

No further observation is needed.

Inclusion criteria

- Patients older than 18 years of age, both genders.
- Patients undergoing simple or complex surgery.
- American Society of Anesthesiologists Classification (ASA) score I to III.

Exclusion criteria

- American Society of Anesthesiologists Classification (ASA) score IV and V.
- Age below 18
- Previous neurological problems affecting EEG
- Dementia
- Use of sedative or drugs that can alter EEG readings
- Patients under head and neck surgery

PROCEDURES AND METHODS**Selection and recruitment of patients**

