Patients are identified as potentially recruitable during the preoperative visit in the preoperative department. The anesthesiologist has to inform adequately patient. After this preliminary check for recruitment criteria, the patient will receive the informing module. The researcher confirms the recruitment criteria during the pre-surgical visit.

Data obtained during the study are confidential and during their presentation will not be discovered information that may reveal the identity of the patient.

Intervention

The authors will perform a prospective study, enrolling patients and performing neuromonitoring using both the standard (FRONTAL) and the alternative (NASAL) montage on each patient.

Evaluation

1. Primary end-point:

- We will monitor and compare processed electroencephalograph (EEG) values (PSi- Patient State Index, SEFL- Spectral Edge Frequency Left, SEFR- Spectral Edge Frequency Right, SR-Suppression Ratio, EMG-Electromyograph, ARTF-Artifact) and EEG waveforms, from nasal and frontal sensors.

2. Other data collected will include:

- Other parameters that will be measure are patient demographics (age, sex, surgery, ASA status, weight, height, BMI).

Plan of study

At least 40 patients are expected to be included after obtaining the approval of Ethical Committee. Patients will be included only if they sign informed consent for study.

The study includes a preoperative visit, perioperative observation.

STATISTICAL ANALYSIS

For each of the two modes of measurement, 1800 data points per subject (1 reading every 2 seconds for 1 hour) per hour will be collected. Assuming a maximum interclass correlation coefficient of .90, a sample size of 40 patients will be required to test the null hypotheses that the two modes of measurement share 95% of their variance via the construction of a 95% confidence interval that ranges no more than +-5%.

Analysis plan

The initial descriptive statistics will describe and summarize the patient characteristics.

Data from the 2 placements will be compared and analyzed using a Bland-Altman analysis and a matched-pair analysis.

Access to data and statistical processing of data will be available and compiled by the author of the study, [name] and CCAD biostatistician, [name].

Safety

Risks and Benefits

This prospective observational cohort study does not present greater than minimal risk for patient.

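### The Bland-Altman and matched-pair analyses have no stated unit of analysis; applied to the individual readings in their standard form, they would understate uncertainty, in most cases severely

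*Combined protocol and SAP*

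**What the plan says.** All references are to the combined protocol and SAP.

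- **Data.** Under Intervention, each patient is monitored by "performing neuromonitoring using both the standard (FRONTAL) and the alternative (NASAL) montage on each patient". Under Statistical Analysis, for each placement, "1800 data points per subject (1 reading every 2 seconds for 1 hour) per hour will be collected".
- **Sample size.** The same section continues: "Assuming a maximum interclass correlation coefficient of .90, a sample size of 40 patients will be required". The stated purpose is to "test the null hypotheses that the two modes of measurement share 95% of their variance via the construction of a 95% confidence interval", with a half-width of at most 5 percentage points. Population adds 20% for drop-out, giving 50 recruited.
- **Analysis.** Under Analysis plan, after a line on descriptive statistics, the whole comparative analysis is: "Data from the 2 placements will be compared and analyzed using a Bland-Altman analysis and a matched-pair analysis".
- **Hypothesis.** Under Research Questions and Hypotheses, the nasal placement "would put the entire montage out of the operative field and would still have corresponding values".

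No section says whether the unit is the reading, an epoch or the patient. None names a mixed model, a cluster-robust standard error, a repeated-measures Bland-Altman form or a per-patient summary.

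**The concern.** Readings taken 2 seconds apart in one patient are not independent. They share that patient's anatomy, sensor contact and anaesthetic course, and adjacent readings resemble each other. The standard Bland-Altman confidence intervals and the standard matched-pair test both assume independent pairs. An analyst who follows the one-sentence plan literally could enter 72,000 pairs as 72,000 independent observations.

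Two things would then go wrong, in opposite directions for the study's claim. The shared-variance CI, the only interval the plan promises, would make agreement look far more certain than 40 patients allow. The matched-pair test would tend to declare a difference where there is none. One report could therefore show near-perfect precision on agreement beside a spurious significant difference. With the unit unstated, the choice also stays open until the data have been seen.

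**Working it through.** **Inputs from the documents.** m = 1800 pairs per patient-hour; k = 40 patients; target shared variance 0.95; 95% CI with half-width at most 0.05.

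**Assumptions, because the documents give no figure.** ICC of the paired differences from 0.01 to 0.90; two-sided 5% level for the matched-pair test; one hour per patient, so 40 x 1800 = 72,000 pairs.

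**1. The plan's own precision target.** Fisher's z on r = sqrt(0.95): z = atanh(r) = 2.178, half-width 1.96/sqrt(n - 3), back-transformed and squared.

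| n | 1.96/sqrt(n - 3) | 95% CI for shared variance | mean half-width |
|---|---|---|---|
| 40 (patients) | 0.322 | 0.907 to 0.973 | 0.0333 |
| 72,000 (readings) | 0.0073 | 0.949 to 0.951 | 0.00071 |

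At patient level, 40 meets the stated target (-0.043/+0.023, both inside 0.05). The figure 40 was not reproduced as a minimum under the formulas tried, but this point does not depend on that. The drop-out step does reproduce: 40/(1 - 0.20) = 50. Ratio of half-widths: 0.0333/0.00071 = about 47.

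**2. Coverage of the pooled shared-variance CI.** Simulated with 40 patients x 1800 exchangeable pairs, with the same ICC for the sum and the difference of the two placements. As a check, the variance inflation for shared variance in this model is about 1 + 1799 x ICC^2, and coverage is about 2 x Phi(1.96/sqrt(inflation)) - 1.

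| ICC | inflation | coverage, formula | coverage, simulated |
|---|---|---|---|
| 0.01 | 1.18 | 93% | 93% |
| 0.10 | 19.0 | 35% | 36% |
| 0.50 | 450.8 | 7% | 7% |
| 0.90 | 1458.2 | 4% | 4% |

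Harm to this interval is small only if clustering is very weak.

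**3. Bias and matched-pair test.** For a mean, the design effect is DE = 1 + 1799 x ICC. The pooled standard error is too small by sqrt(DE), and the pooled test rejects a true zero difference with probability 2 x (1 - Phi(1.96/sqrt(DE))).

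| ICC | DE | standard error too small by | rejection of a true zero difference |
|---|---|---|---|
| 0.01 | 19.0 | 4.4 | 65% |
| 0.10 | 180.9 | 13.4 | 88% |
| 0.50 | 900.5 | 30.0 | 95% |
| 0.90 | 1620.1 | 40.3 | 96% |

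Simulation (20,000 runs) agrees: 64.7%, 88.2%, 94.8% and 95.9%. A t-test on 40 patient means rejects 4.7% to 4.9% of the time.

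**4. Serial correlation alone.** Suppose there is no patient effect, and autocorrelation phi = exp(-2/T) at 2-second spacing. Then DE = (1 + phi)/(1 - phi) - 2 phi (1 - phi^m)/(m (1 - phi)^2). Assumed time constants T of 10, 30 and 60 seconds give DE of 10.0, 29.8 and 59.0, and rejection of 54%, 72% and 80%.

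**5. The limits of agreement.** With equal records, the pooled SD is 0.98 to 1.00 of the true SD, so the limits barely move. Their uncertainty does change: a nominal 95% CI for the upper limit, computed from pooled readings, covered 19%, 7% and 4% of the time at ICC 0.10, 0.50 and 0.90.

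**The case against.** The strongest reply is that every figure above describes an analysis the plan does not say it will run. The study is sized in patients, a correlation coefficient sits beside that count, and a biostatistician is assigned. A patient-level analysis fits the text at least as well as a pooled one. This stands: the fault is an unspecified unit, not a stated wrong analysis. It does not remove the point, because the two named methods default to independent pairs and nothing in the plan overrides that default.

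Three stronger readings are tempting, and the documents do not support them.

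- **That the .90 fixes an effective sample size.** Read as within-patient clustering, it would give 72,000/1620.1 = 44.4 units. But that design effect is for a mean; for shared variance the factor is about 1458, giving about 49. The plan also writes interclass, in a sentence about two modes sharing variance, so .90 may be the correlation between placements. No effective sample size should be read from it.
- **That pooling offers an easy route to false validation through the test.** The matched-pair error counts against the hypothesis of corresponding values. The risk in the sponsor's favour is the over-precise agreement interval.
- **That the reported limits would be wrong.** With equal record lengths they barely move. This was checked only for equal lengths. Under Duration of evaluation, patients are followed from induction until shortly after extubation. If whole cases are pooled, longer operations get more weight and the estimates could shift.

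**Conclusion.** The point holds in conditional form and should be fixed before analysis. The plan names two methods that assume independent pairs, for data with 1800 pairs per patient-hour, and does not state the unit.

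If the methods are applied to the readings, the promised CI is about 47 times too narrow relative to the interval for 40 independent patients, and it loses most of its coverage unless clustering is very weak. CIs for the bias, if reported, are 4.4 to 40 times too narrow, and those for the limits are too narrow as well. The matched-pair test is close to uninformative over the whole assumed ICC range.

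These sizes rest on assumed ICCs, an assumed 5% level, exchangeable readings (or the stated autocorrelation) and one hour per patient. A reader might infer that the plan commits to pooling, or that 40 patients is too few for its precision target. The text supports neither.

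**What to change.** Add three or four sentences to the Analysis plan:

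1. The patient is the unit of inference.
2. The bias, the limits of agreement and their CIs come from a Bland-Altman analysis for multiple readings per subject, using either a random patient effect (with within-patient autocorrelation) or resampling of whole patients. Choose one in advance.
3. The CI for shared variance comes from resampling whole patients.
4. The matched-pair test uses one summary difference per patient (n = 40). Its non-rejection is not evidence of agreement.

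Also say whether one hour or the whole case is analysed and, if the whole case, how unequal record lengths are weighted.

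**Cost.** No new patients or data, and a little more programming. Intervals will be wider, which is the honest result. With 40 patients a percentile bootstrap covers slightly under 95% (simulated 92% to 94%). For the bias, a t-interval on patient means avoids this (simulated about 95%).
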